Aim 2: Test a sustainable model of CHTC implementation in real world adolescent HIV clinics. In line with the implementation science focus of SIU U19, we utilize the EPIS to guide our implementation strategy. We will work with SIU Analytic Core's (AC) health-economist, [name], to conduct cost-effectiveness analyses to inform implementation decision-making. In collaboration with SIU ISC, we will document provider feedback to training and intervention materials to modify materials and create training packages for broad dissemination.

We will achieve our aims over two phases of the study.

PROTOCOL TITLE:

Phase 2 (n=36 couples): involves a pilot randomized control trial (RCT) to evaluate the acceptability, feasibility, and preliminary efficacy of these adjunct components.

Phase 3 (n=200 individuals): involves a CET comparing the most promising intervention package from Phase 2, consisting of individual MI, ACT video+ a recognition survey, and CHTC, compared to individual HIV testing and counseling (IHTC) delivered as usual. Participants in either condition can come as an individual or with their partner or come first as an individual and then bring their partner. This phase is focused on Implementation and Sustainment phases of the EPIS model informed by outcome analyses, cost analyses, and feedback from youth and ATN staff.

Phase 3 has now been added to this protocol document.

Hypothesis: The primary hypothesis is that because of developing skills in self-management and assertive communication, inclusion of adjunct components will be associated with clinically significant decreases in HIV transmission risk behavior as compared with partnered YMSM who receive individual testing and counseling (only). Secondarily, we propose that these intervention effects will be mediated by assertive communication skills.

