6.0 Procedures Involved*

Enrollment and Consent: Utilizing enrollment procedures established within ATN, clinic staff will invite YMSM who present for HIV testing services the opportunity to screen. These interested index partners will complete a brief iPad eligibility screener.

For Phase 2, IF ELIGIBLE, THE SCREENER WILL RANDOMIZE THEM TO COMPLETE THE BASELINE AS A COUPLE OR AN INDIVIDUAL.

If randomized to individual, staff will schedule a baseline assessment for the invited youth. If randomized to couple, staff will schedule a baseline assessment for the invited youth at a time both they and their relationship/romantic partner are available. Partners

PROTOCOL TITLE:

will independently complete informed consent at the beginning of the baseline visit, prior to assessment following ATN-wide established protocols.

FOR PHASE 2, IF THE YOUTH IS RANDOMIZED TO COMPLETE THE BASELINE AS A COUPLE, AND THEY INDICATE THAT THEY WILL BE UNABLE TO HAVE THEIR PARTNER COME FOR THE APPOINTMENT, THEY WILL BE ALLOWED TO COME TO THE BASELINE AS AN INDIVIDUAL.

For Phase 3, study sites are given the options to deliver the intervention in-person as usual, or entirely remote delivery. This is to allow sites more flexibility surrounding COVID-19 closures and restrictions, which vary by site.

For Phase 3, index partners will be able to choose to attend their baseline appointment on their own or with their partner. While scheduling the baseline, staff will ascertain whether the participant is planning to come in alone or with their partner so they can reserve adequate time, space and resources for the appointment. Regardless of whether the index partner attends alone or with their partner, after the participant(s) complete the survey at the beginning of the baseline appointment, the index partner will be randomized to the We Test intervention or individual HIV testing (IHTC) as usual. If alone and randomized to the We Test intervention, the index partner will participate in the intervention as an individual. If both members of the couple attend and are randomized to We Test, they will participate in the intervention as a couple. If both members of the couple attend and are randomized to IHTC, they will each receive IHTC as usual. The index partner who participates as an individual (in either condition) will be offered the opportunity to bring their partner to participate in the WeTest. The partner will be enrolled into the same condition as the index partner.

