Baseline Visit – PHASE 2 (up to \$50)

1. Informed Consent process
2. STI testing (\$20)
3. CASI survey (\$10)
4. Randomization to one of three conditions (phase 2)
5. Session 1 (phase 2): will occur at this time in accordance with the randomized condition.
 - a. Condition 1: CHTC
 - b. Condition 2: ACT videos + CHTC
 - c. Condition 3: MI-CST + ACT videos + CHTC

FOR COUPLES WHO ARE ASSIGNED TO A CONDITION THAT INCLUDES VIDEOS, PARTICIPATING COUPLES WILL WATCH THE VIDEOS SEPARATELY. AFTER VIEWING THE VIDEOS SEPARATELY, A VIDEO RECOGNITION SURVEY (ATTACHED) IS COMPLETED BY THE COUPLE TOGETHER.

Baseline Visit – PHASE 3 (up to \$50)

1. Informed Consent process
2. CASI survey (\$30)

PROTOCOL TITLE:

3. Randomization
4. HIV testing (\$10)
5. STI testing (\$10)
6. Session 1: will occur at this time in accordance with the randomized condition.
 - a. Condition 1: individual HIV testing (IHTC) as usual condition
 - b. Condition 2: We Test intervention

Randomization Stratification: Randomization will be stratified by Site, Age (either partner under 18 vs both 18 & older), Race/Ethnicity (Both White vs not both White) and whether the index partner attended individual vs couple.

After completing the baseline assessment for both Phases 2 and 3, YMSM will complete follow-up assessments a month after baseline, and 3 months after baseline. In Phase 3, participants will also complete assessments at 6-months post-baseline. Online CASIs will be completed at each follow-up either at home or in-office. In addition, STI and HIV testing will occur at the 3-month and 6-month follow-ups. All follow-ups will be conducted individually to facilitate retention, even if the couples dissolve.

Immediate Post-Test Assessment (1 month after BL)

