1.2.1 Analytic Plan

All primary outcome variables will be tested in the context of a multilevel growth model, which accounts for the nesting of individuals within couples. In order to capture within-individual change over time, we will utilize a latent growth curve approach to modeling follow-up data. At the individual level (Level I), models will include an intercept and linear slope component to represent the initial value and change over time in each participant's outcome. We will explore the inclusion of quadratic components as indicated by model fit. Mplus provides the flexibility to accommodate count and dichotomous outcomes. Growth factors will then be regressed on intervention condition at the couple level (Level II) and the effect of the intervention will be evaluated by examining the regression coefficient (and associated *p* value) associated with intervention condition for each of these factors.

Secondary analyses of individually reported self-management and dyadic functioning as potential mediators of the intervention's effect on TRB will specify growth factors for self-management, dyadic functioning, and communication skill scores during the follow-up period. In this manner, growth factors for the outcome can be regressed on growth factors for the putative mediator. Intervention effects (a couple-level predictor) will be determined by examining regression coefficients associated with intervention in the prediction of growth factors for both

the outcome of interest and mediator. For significant direct effects, indirect path from intervention communication will be tested using bootstrapping tests of mediation. Where outcome distributions prevent bootstrapping, we will utilize a model constraint approach to evaluate significance of indirect effects. The product of constituent direct effects is constrained as zero. The overall model fit under this constraint is compared to one where the constraint is not specified. A statistically significant reduction in fit associated with constraint represents evidence that indirect effects differ from zero[53].

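### Phase 3 We Test is delivered to couples or to one person, but SAP 1.2.1 estimates a single condition effect with no attendance term, so the analysis cannot show whether the effect holds under both forms of delivery

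*Protocol*

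**What the plan says.** **The package.** Protocol 2.0 describes the Phase 3 experimental condition as "consisting of individual MI, ACT video+ a recognition survey, and CHTC, compared to individual HIV testing and counseling (IHTC) delivered as usual". CHTC is, by its name in the Protocol's list of abbreviations, a couples service.

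**Who attends.** Protocol 2.0 leaves this to the participant: "Participants in either condition can come as an individual or with their partner or come first as an individual and then bring their partner".

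**How it is delivered.** Protocol 6.0 makes delivery follow attendance. For a solo attendee: "If alone and randomized to the We Test intervention, the index partner will participate in the intervention as an individual". For a couple: "If both members of the couple attend and are randomized to We Test, they will participate in the intervention as a couple". The comparator is individual in both cases: "If both members of the couple attend and are randomized to IHTC, they will each receive IHTC as usual". An index partner who starts alone, in either condition, "will be offered the opportunity to bring their partner to participate in the WeTest", and the partner then joins the index partner's condition.

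**Randomisation.** Allocation follows the baseline survey, so attendance is already settled by then. The stratification factors in Protocol 6.0 include "whether the index partner attended individual vs couple".

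**Analysis.** SAP 1.2.1 states: "Growth factors will then be regressed on intervention condition at the couple level (Level II". The intervention effect is read from that coefficient. The section has no attendance term, interaction, subgroup or estimand statement.

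**The concern.** Attendance changes what the experimental arm receives, while the comparator keeps the same form. A single condition coefficient averages over the two forms of delivery, with weights set by however many youth happen to come alone. The documents neither fix nor forecast that share.

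The result would therefore answer one question: what offering We Test did in this mix of attendees. It would not show whether the effect is present when a couple attends, when one person attends, or in both cases. Aim 2 depends on that. Its implementation and cost-effectiveness work concerns a service that a clinic may deliver to two people or to one, and Protocol 5.0 plans to package for dissemination whatever proves effective. A null pooled result would not distinguish an ineffective package from one that works in a single mode. A positive pooled result would not say which mode to roll out.

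**Working it through.** **1. Delivery by arm and attendance (Protocol 6.0)**

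| Attendance at randomisation | We Test arm | IHTC arm | Partner may join later |
|---|---|---|---|
| Solo | Package given to one person; video and survey done alone; form of the CHTC component not described | IHTC | Yes, into the same condition |
| Couple | Package given to the couple | IHTC for each partner | Not applicable |

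Only the experimental side differs between the rows. Each row is a randomised contrast, because attendance precedes allocation and is a stratum. Partner-later entry is a third form, and it is decided after randomisation.

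**2. What the model estimates.** An intercept and a linear slope (a quadratic term if fit suggests it) are each regressed on condition. Under SAP 1.2 and the Equivalency Tests section, extra covariates enter through the attrition analyses, so attendance is not a planned term. Pooling is inferred from this silence. The SAP text treats everyone as part of a couple.

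**3. The plan's own figure.** SAP 1.2.2 states power above .80 for 144 couples (288 individuals, at least 232 retained). Retention is 232/288 = 80.6%. The simulation cannot be reproduced, because the control rate, within-couple correlation, growth variances and allocation are not given. A simple two-proportion check (OR 0.44, 116 per arm, two-sided 5%, one time point, independent observations) gives power of 0.58, 0.73, 0.82 and 0.86 at control rates of 0.20, 0.30, 0.40 and 0.50. The stated figure is neither confirmed nor contradicted. For this point, what matters is that none of the effect sizes cited there describes solo We Test. The 0.44 comes from couples aged 18–29 and compares ACT + CHTC with CHTC alone. The MI effect is against a psychoeducation control.

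**4. Illustration of pooling.** Assumptions, not figures from the plan:
- OR 0.44 for We Test versus IHTC among couple attendees
- solo share *s* of 30%, 50% or 70%
- solo log-OR equal to *f* times the couple log-OR

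Pooled log-OR = [(1 − s) + s·f] × ln 0.44, with ln 0.44 = −0.821.

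| Solo effect | s = 30% | s = 50% | s = 70% |
|---|---|---|---|
| None (f = 0) | exp(0.70 × −0.821) = 0.56 | exp(0.50 × −0.821) = 0.66 | exp(0.30 × −0.821) = 0.78 |
| Half (f = 0.5) | exp(0.85 × −0.821) = 0.50 | exp(0.75 × −0.821) = 0.54 | exp(0.65 × −0.821) = 0.59 |
| Same (f = 1) | 0.44 | 0.44 | 0.44 |

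Cross-check by averaging event rates instead of log-odds, with control rate 0.30 and s = 50%. The couple rate is 0.159. With f = 0 the mean rate is (0.159 + 0.300)/2 = 0.229, so OR 0.69. With f = 0.5 the mean rate is 0.190, so OR 0.55. Both are close to 0.66 and 0.54.

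**5. Precision of a split analysis.** At the same retention, 200 individuals give 200 × 0.806 = 161, or about 40.25 per arm in each stratum if half attend alone. The variance of a log-odds is 1/[n·p(1 − p)]. With control rate 0.30 this is 0.118 for a control cell and 0.186 for the couple We Test cell.
- Couple stratum: SE = √(0.118 + 0.186) = 0.552. A 95% interval around 0.44 runs from about 0.15 to 1.30.
- Interaction (OR 0.44 in couples, 1.0 solo): SE = √(3 × 0.118 + 0.186) = 0.736, and power = Φ(0.821/0.736 − 1.96) = 0.20. At control rates of 0.20 and 0.40 it is 0.16 and 0.23.

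These figures ignore within-couple correlation and the repeated measures.

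**The case against.** The strongest reply is that Phase 3 is a comparative effectiveness trial whose design deliberately allows either form of attendance. The pooled randomised contrast is then a valid estimate of offering We Test under that design, and dependence on the case mix is normal. This stands, and it is why the pooled effect should remain the main result. But the SAP does not state that estimand, and stating it does not supply the information by mode.

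Stratified randomisation is a weaker reply. It balances the arms within each mode but puts nothing into the model. A stratum main effect alone would still leave one condition effect.

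A reader might infer that solo attendees receive only MI, the video and an ordinary individual test, so that two different treatments are being pooled. The documents do not say this. They describe solo viewing of the video and are silent on the CHTC component. The Protocol 2.0 hypothesis credits the adjunct components, which Protocol 5.0 identifies as ACT and MI-CST, and nothing indicates that solo attendees lose either. An equal effect in both modes is therefore possible and belongs in any illustration.

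Two limits on a split analysis also stand: the interaction is underpowered, and attendance is self-selected. Finally, the SAP text predates solo entry (SAP 1.2 still names CHTC only as the comparator), so this gap is one consequence of a plan not updated for Phase 3. It still needs its own repair.

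**Conclusion.** The concern holds as a gap in interpretation, not as bias. The plan randomises within attendance mode, varies the experimental delivery by mode, and then reports one effect that cannot show whether both modes work.

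The size is unknown because the documents give neither the solo share nor any effect of solo delivery. On an assumed couple OR of 0.44 and 30–70% solo, the pooled OR is 0.56–0.78 with no solo effect, 0.50–0.59 with half the log-OR, and 0.44 with an equal effect. These ranges should not be merged into one range attributed to the solo share, since the assumed solo effect changes as well. The 0.44 itself is borrowed from a comparison with CHTC alone.

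Two stronger conclusions are tempting and unsupported. One is that the pooled estimate applies to no one: it applies to the offer of We Test at this trial's mix. The other is that claims about the package should rest on couples alone: that contrast tests the whole package against IHTC in a self-selected group and does not isolate CHTC. The change is worth making, but the gap does not invalidate the main comparison.

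**What to change.** In SAP 1.2.1:
- Keep the pooled condition effect as the main result, and state that it is the effect of offering We Test versus IHTC averaged over attendance mode.
- Add attendance at randomisation (solo or couple) as a main effect in the growth-factor regressions. Add the condition-by-attendance term in a second, supportive model, so that the condition coefficient in the main model remains the pooled effect.
- Report the condition effect with its confidence interval in each stratum beside the pooled effect.
- Define strata as randomised. An index partner who later brings a partner stays in the solo stratum, which then estimates We Test offered to solo attendees, including any later partner entry.
- Say that the interaction is underpowered and that, with self-selected attendance, a difference between strata does not isolate the contribution of CHTC.

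In the Protocol, reconcile the package description in 2.0 with solo delivery in 6.0, so that it is clear what solo attendees receive as the CHTC component.

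The cost is SAP and protocol wording plus two model terms. Attendance is already recorded for stratification, so no new data are needed. The stratum estimates will be imprecise, as the interval of about 0.15 to 1.30 in the working shows.

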1. CASI (\$30)

Three Month Follow-Up (up to \$50)

1. CASI (\$30)
2. HIV testing (\$10)
3. STI testing (\$10)

Six Month Follow-Up (\$50)

1. CASI (\$30)
2. HIV testing (\$10)
3. STI testing (\$10)

All ATN clinics in this project are currently performing HIV testing as part of the services they offer to the local community. Therefore each clinic has a protocol in place to deliver HIV positive results and link patient who test HIV positive to timely access to health care, including antiretroviral therapy. Participating clinics will be performing HIV testing as part of their routine services and will follow their local protocol for delivering HIV positive results for those testing positive for HIV. Meaning of the test results will be discussed with all youth who test for HIV prior to screenings.

Participants who test positive for HIV while enrolled will be referred for a confirmatory HIV test when needed. Research staff trained in HIV testing and counseling will discuss the meaning of the HIV test results and explain the importance of timely access to health care, including antiretroviral therapy.

Participants WHO RELOCATE OR ARE UNABLE TO ATTEND AN ATN SITE AFTER BASELINE WILL HAVE THE OPTION for at home HIV and STI testing or TESTING THROUGH a central lab such as Quest. SUCH PARTICIPANTS WHO TEST

PROTOCOL TITLE:

HIV positive at a follow up assessment will receive the result from a member of PRIDE team who are key personnel on the project and are trained in HIV testing and counseling. See the attached PRIDE Response Management Plan which includes the protocol for delivering HIV positive results. Due to COVID, there are now at home and central lab testing options for Baseline and intervention testing.

Participants who test positive for an STI at baseline or follow up assessments will be referred using the ATN clinics' local protocol for positive STI results if STI testing occurs at one of ATN clinics. Participants who test positive for an STI through at home or central lab testing such as Quest will follow the attached protocol for delivery of positive STI results. **STI RESULTS WILL BE SENT TO THE PARTICIPANT VIA A SECURED WEBPAGE AND PARTICIPANTS WILL RECEIVE A UNIQUE PASSWORD TO VIEW THEIR RESULTS.**

For at home HIV/STI testing, kits may be mailed to a home address. Research staff will allow kits to be shipped to an alternate location deemed as a safe space, such as a youth center, and will require youth to speak with a trained staff member to ensure these arrangements are both safe and allowable. The at-home testing kit will come either from Molecular Labs or as a OraQuick HIV test.

If a couple comes in together they will view an assertive communication training video separately and complete a video recognition survey together after. If a participant comes in without their partner, they will view the ACT video and complete the video recognition survey after.

All compensation is payable as cash or gift card based upon site restrictions.

Specimen Collection: HIV data will be collected via a blood draw or oral swab using a HIV rapid test and biomarkers STI will be collected via urine and rectal screen. The only purpose of the collected data is research. Participants who test positive for STI's will be reported to the local health department in accordance with state laws for surveillance purposes. Participants who test positive while enrolled in We Test will be referred for a confirmatory HIV test and care following standard procedures at the clinic. Following standard ATN procedures, data will be coded with a unique study ID number at the time of enrollment, unrelated to their name or other personal identifying information; all specimens and survey data will be labeled with this unique identifier to provide anonymization of the data. The people who will have access to the data include members of the research team. Test results will not be shared with individuals outside of the research team. For at home testing procedures, we will share name and address with Molecular Labs for shipping the test kit only. Anonymized data will be coordinated with the broader ATN using established multi-site data sharing avenues.

7.0 Data and Specimen Banking*

Data for Future Use

Participants consent to these procedures as part of the consent/assent process.

PROTOCOL TITLE:

The research team, authorized staff, and government agencies that run this type of research may have access to research data and records in order to check on the research. Research records given to approved researchers will be de-identified. If a researcher requests the data, they will be granted special permission from the Research Compliance Administrator. Data collected during this research study may be used for future research purposes. The data stored will be de-identified.

Data that cannot be linked to participants (i.e., de-identified data) will be kept indefinitely; this data will be saved for future use and may be shared with other researchers.

Biological samples collected for the purposes of this study will not be used to conduct any future research. They will be destroyed after analysis is completed.

At the end of the study data collected will be made available, in accordance with the NIH Data Sharing Policy (http://grants.nih.gov/grants/policy/data_sharing). These data will be saved for future use and may be shared with other researchers. By participating in this study, you are agreeing to allow us to save and share your data anonymously.

8.0 Sharing of Results with Subjects*

Phase 2 and Phase 3: HIV and STI Testing Results

Rapid HIV tests are performed, and results shared with the participants at both the baseline and 3-month, and 6-month (Phase 3 only) assessments. HIV test results are delivered in-person with referrals for PrEP/PEP and linkage to care (in the event of a positive test result). STI test results are sent individually to the participant via email. Results are entered into an online Qualtrics portal and sent to participant's email address where they can view and save their results. The participant can confidentially view their STI results through the Qualtrics portal.

For at-home Testing- Rapid HIV testing is performed with the person over ZOOM during the intervention. STI testing samples are collected and returned to the central lab for processing. Results are provided to the study team via a secure website. Those results are entered into an online Qualtrics portal and sent to participant's email address where they can view and save their results. The participant can confidentially view their STI results through the Qualtrics portal.

In Phase 3, we will be reporting positive STI results to departments of health in New York, Michigan, and California for surveillance purposes. Reporting of names for this purpose is state law and not exempted by research studies. We will inform the participants in the consent form that this will occur. Name, Date of Birth, and phone number will be reported.

All results are not shared with any other individuals.

PROTOCOL TITLE:

